Table 5. Outcomes for the peer PrEP referral + HIVST delivery pilot and measured at Month 1. * primary		Metric of success: Allow seamless progression to trial	
Outcome:	Details:	Reported:	
PrEP initiation*	Prop. of referred peers that initiated PrEP*	Peers and PrEP users	40% of those followed up (n≥19)
PrEP referral	No. of peers referred to PrEP	PrEP users	≥3 peers per PrEP user (n≥48)
HIVST use	Prop. of referred peers that used HIVST	Peers	75% of those followed up (n≥36)

605
 606 FGDs. Transcripts will be reviewed separately by two or more qualitative researchers, who will ensure
 607 completeness. These researchers will immerse themselves in the data through repeated readings of the
 608 transcripts and create a preliminary codebook of inductive^{43,44} and deductive^{45–47} codes to capture the
 609 experiences of AGYW regarding a peer PrEP referral + HIVST model including barriers and facilitators
 610 (Objective 3). A sample of transcripts will be double coded independently by two or more researchers,
 611 with coding discrepancies identified and resolved via consensus. During this process, the codebook will
 612 be refined, with existing codes combined, separated, or eliminated and new codes added as needed to
 613 capture emerging themes.^{48,49} Thereafter, remaining transcripts will be coded in Dedoose (Los Angeles,
 614 California, USA) or Nvivo 12 (QSR International, Melbourne, Australia). We have extensive experience
 615 analyzing qualitative data to inform intervention development.^{50–72}

616 *Participant retention and withdrawal*

617 The Thika research site will develop retention methods tailored to and most efficient for the local study
 618 settings. Retention activities may include explanation of the study schedule (i.e., return for follow-up after
 619 one month) and procedural requirements during the informed consent process. Further, peers referred
 620 to the study, will be contacted and directed to the PHRD study site for follow-up or will be visited (e.g., at
 621 home) by PHRD researchers. However, should the aimed sample size not be attained (e.g., < 75%
 622 referral rate), then alternative follow-up strategies may be implemented including 1) giving peers mobile
 623 money conditional on texting researchers their contact information or 2) having PrEP users report
 624 outcomes for their peers.

625 Participants may voluntarily withdraw from the study for any reason at any time. The site investigators

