657 that receive the peer PrEP referral + HIVST intervention delivered by the peer providers. For reporting
658 purposes, we will also refer to peer providers as “index peers” and peer clients as “referred peers.”

659 We will recruit 80 young female peer providers from public healthcare clinics delivering PrEP in Kiambu
660 County and neighboring Counties using established PHRD site techniques. These participants will further
661 refer 4 peer clients each to PrEP for a maximum 320 potential peer clients.

662 Eligibility criteria.

663

664 **Peer providers.** Eligible peer providers will be: i) female, ii) ≥ 16 to 24 years old (including emancipated
665 minors ≥ 16 to 17 years³⁶), iii) must have refilled or initiated PrEP (i.e., been dispensed PrEP), iv) are able
666 to identify 4 peers at risk of HIV infection who may be interested in PrEP, v) not currently enrolled in
667 another HIV study, and vi) are able and willing to be randomized to the intervention, complete research
668 activities, and provide written consent (**Table 6**). Due to the nature of the training intervention which
669 includes slides, quizzes, and other activities that involve reading and writing, peer providers will be
670 considered ineligible if they do not have basic literacy skills. Due to some challenges recruiting young
671 female peer providers in the Aim 1 pilot, we made some modifications to the inclusion criteria in this
672 section, including reducing the duration of PrEP use and dropping the requirement for PrEP disclosure.

673

674 **Peer clients.** Eligible peer clients will be: i) female, ii) ≥ 16 to 24 years old (including emancipated minors
675 ≥ 16 to 17 years³⁶), iii) referred by a peer provider to initiate PrEP, and iv) are able and willing to provide
676 informed consent.

677

678 **Recruitment strategies.** **Peer providers.** Peer providers will be recruited through a multipronged approach
679 that will include recruitment through other ongoing PrEP research projects, and from nearby public health
680 facilities implementing PrEP programs, such as, workshops for healthcare workers, use of IEC materials,
681 and working with community health workers to identify potential participants. Peer providers will be

682 compensated 300 KES (~\$2.70 USD) and be reimbursed for travel at their baseline appointment and
683 again at their 3-month follow-up appointment. No travel reimbursement at follow-up will be provided if

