 844 initiation. At a subset of in-person visits, a DBS collected from a finger prick or venous blood will be
 845 prepared at the site and stored at -20 degrees Celsius. Prior to storage, the DBS will be left to air-dry for
 846 at least 2 hours and thereafter placed in low gas-permeability Ziploc bags with a desiccant pack to reduce
 847 humidity thus maintaining integrity of the sample. The DBS samples will be labeled with the de-identified
 848 participant ID and will be shipped outside Kenya for temporary storage at Fred Hutchinson Cancer Center
 849 (Washington State, USA) and forwarded to Molecular Testing Labs (Washington State, USA) for TDF
 850 and FTC level testing. The shipped samples will be stored until the testing is completed and results
 851 confirmed. These outcomes are expanded on in the following section. It is possible that DBS samples
 852 will not be sent for testing if we do not achieve the target sample size of 23 peer clients per study arm.

853

854

855

856

857

858

859 **Data Analysis**860 All outcomes will be measured at study follow-up (Month 3) (**Table. 8**).

Table 8. Outcomes for the peer PrEP referral + HIVST delivery trial, measured at 3 months. * = primary					Metrics of success: for R01 progression
Outcome:	Details:	Outcome type:	Reported:	Measures:	
PrEP initiation*	Prop. of clients initiating PrEP	Adoption (clients)	Provider	No. of new clients using PrEP / No. of referred clients	>20% increase
PrEP referral	No. of clients referred to PrEP	Adoption process (providers)	Provider	No. of clients referred to PrEP / No. of referred clients	>50 more peers
PrEP continuation ¹	Prop. of clients refilling PrEP (any) since referral	Adoption secondary (clients)	Provider	No. of clients with >1 PrEP clinic visits / No. of referred clients	>20% increase
PrEP continuation ¹	Prop. of providers refilling PrEP (any) in the past 3 months	Adoption secondary (providers)	Provider	No. of providers with 1+ PrEP clinic visits in past three months / No. of providers	>20% increase
PrEP adherence	Median of Wilson et al's 0-100 point adherence score	Adoption secondary (clients)	Client	Median score	>20% increase
HIVST use	Prop. of clients in the formal arm that used a HIVST.	Adoption process (clients)	Client	No. of clients self-reporting use of HIVST / No. of referred clients	≥90% (n=144 – formal arm)

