 904 predictor: study arm; standard errors adjusted for clustering by peer provider). All analyses comparing
 905 randomization arms will be intention-to-treat, complete case analyses conducted at the unit of the
 906 individual (either peer provider or peer client). The primary comparison will be formalized peer PrEP
 907 referral + HIVST delivery versus informal peer PrEP referral (the standard of care). For analyses
 908 conducted at the level of the peer client, we will adjust standard errors for clustering at the peer provider
 909 level. We will use mixed-effect logistic regression models to measure risk ratios. All statistical test with 2-
 910 sided p-values <0.05 will be considered statistically significant. We will complete all analyses in R and
 911 STATA.

912 *Sample size*

913 If we assume that peer providers refer 75% of the targeted peer clients, this leaves us with three clients
 914 per peer provider, or 240 peer clients in total. We performed power calculations for our primary outcome,
 915 the proportion of referred peer clients who initiated PrEP at three months, in Stata 16.1 using methods
 916 for cluster-randomized trials, where each cluster is a peer group of one peer provider and three peer
 917 clients (**Figure 10**). **Table 10** shows the power we have to attain to detect various increases in the
 918 proportion of peer clients who initiated PrEP in the formal peer PrEP referral arm + HIVST (intervention
 919 group) vs. the informal peer PrEP referral arm (standard of care group). For our power calculations, we
 920 assumed 40 clusters (peer providers) per arm, 3 sampling units (peer clients) per cluster, and an intra-
 921 cluster correlation coefficient (ICC) of 0.05, which is standard for cluster-randomized controlled trials.
 922

925

Fig. 10. Power calculation to detect increase in the percentage (%) of referred peer clients initiating PrEP in the intervention group.

926

927

Table 10. Increase in the % of referred peer clients initiating PrEP in the intervention group. ICC: 0.05; clusters (providers) per arm: 40; units (clients) per cluster: 3 (75% of suggested clients referred)

Power (%)	Standard of care (%), p1	Intervention (%), p2	Increase (%), p2-p1
70	30	46.3	16.3
	40	56.8	16.8
	50	66.5	16.5
	60	75.7	15.7
	70	84.1	14.1
	80	91.7	11.7
80	30	48.4	18.4
	40	58.9	18.9
	50	68.5	18.5
	60	77.5	17.5
	70	85.7	15.7
	80	92.9	12.9
90	30	51.4	21.4
	40	61.7	21.7
	50	71.2	21.2
	60	79.9	19.9
	70	87.8	17.8
	80	94.5	14.5

928

929

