Study groups:	
Intervention: Enhanced peer referral (previously formal peer referral)
 
 
• Index peers randomized to the enhanced group will receive the package of implementation strategies below and be encouraged to refer four peers to PrEP: 
 
○ A one-day training on HIVST & PrEP and how to have conversations about and refer peers to PrEP service
 
○ PrEP informational brochures (n=4, 1 per peer)
 
○ HIVST kits (n=8, 2 per peer)
 
○ PrEP referral cards (MOH-style), with information on nearby facilities delivering free PrEP services (n=4, 1 per peer)
 
 
 
• Referred peers referred to PrEP services by index peers in this group should receive the described package of implementation strategies to support PrEP referral.
 
 
Control: Standard peer referral (previously informal peer referral):
 
 
• Index peers randomized to the standard group will be encouraged to refer four peers to PrEP services using existing informal word-of-mouth referral, common among AGYW. They will receive: 
 
○ PrEP referral cards (MOH-style), with information on nearby facilities delivering free PrEP services (n=4, 1 per peer)
 
 
 
• Referred peers referred to PrEP services by index peers in this group will be referred to PrEP services informally, as is ongoing in Kenya.
 

Sample size:	
400 enrolled index and referred peers in total*
 
 
• 80 index peers
 
• Up to 320 referred peers
 
 
*The enrollment numbers for referred peers may be lower due to challenges in getting provide their contact information at the time of peer referral. Primary outcomes among referred peers will be reported by index peers in index peer follow-up surveys.

Follow-up:	3 months from either the time of intervention delivery (index peers) or time when study staff received their contact information (referred peers)
Study sites:	Three counties in Central Kenya: Kiambu, Nairobi, and Murang'a (in the area surrounding the PHRD research clinic in Thika)

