#### **5. Sample size justification**

##### **5.1. Sample size calculation**

If we assume that index peers refer 75% of suggested referred peers, this leaves us with three clients per peer provider, or 240 referred peers in total. We performed power calculations for our primary outcome, the proportion of referred peers who initiated PrEP at three months, in Stata 16.1 using methods for cluster-randomized trials (cRCTs), where each cluster is a peer group of one index peer and three referred peers.

**Table 6** and **Figure 3** shows the power we attain to detect various increases in the proportion of referred peers who initiated PrEP in the enhanced group versus the standard. For our power calculations, we assumed 40 clusters (index peers) per group, 3 sampling units (referred peers) per cluster, and an intra-cluster correlation coefficient (ICC) of 0.05, which is standard for cRCTs, we might have 80% power to detect a difference of 17% PrEP initiators between the enhanced group (80%) and standard group (63%).

**Figure 3. Power calculation to detect increase in the percentage of referred peers initiating PrEP in the enhanced group compared to the standard.**

**Table 6. Increase in the % of referred peers initiating PrEP in the enhanced group compared to standard under different assumptions.**

Power	Standard: % PrEP initiation	Enhanced: % PrEP initiation	% increase
80%	57.1%	75.0%	17.7%
	63.0%	80.0%	17.0%
	69.1%	85.0%	15.7%
85%	55.8%	75.0%	19.2%
	61.7%	80.0%	18.3%
	67.9%	85.0%	17.10%
90%	54.2%	75.0%	20.8%
	60.1%	80.0%	19.9%
	66.4%	85.0%	18.7%

Assumptions: ICC: 0.05; clusters (providers) per arm: 40; units (clients) per cluster: 3 (75% of suggested clients referred)

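### The peers-referred outcome is printed as a ratio that always equals 1, and the SAP's only non-binary estimator does not suit a 0–4 count with one value per index peer

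*Protocol*

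**What the plan says.** Protocol, Data Analysis, Table 8 lists PrEP referral as a process outcome reported by providers (the SAP's index peers). Its Details column names a number of clients. Its Measures column reads "No. of clients referred to PrEP / No. of referred clients", and its progression metric reads ">50 more peers". The comparator is not written; I read it as intervention minus control.

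The scale is bounded. Under Aim 2, Study population, providers are to "refer 4 peer clients each to PrEP for a maximum 320 potential peer clients". SAP Table 1 gives index peers in both groups "PrEP referral cards (MOH-style), with information on nearby facilities delivering free PrEP services (n=4, 1 per peer". There are 40 index peers per arm.

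SAP 4.2 says the process outcomes will be compared between study groups to help interpret the primary and secondary results. SAP Table 4 defines peers referred as a number reported by index peers at Month 3, and its note then calls every outcome in the table binary. SAP 10.2 gives two estimators: risk differences for binary outcomes, and median differences from linear quantile mixed models for continuous ones. Both carry index-peer random effects.

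**The concern.** Taken as printed, the Table 8 measure cannot differ between arms, and the SAP note points a count towards a risk difference although no success threshold is defined. An analyst who sees past both slips and treats the outcome as a number is left with the median-difference rule. That rule was written with the adherence score in mind, which has many values and several referred peers per index peer. Referral has five possible values and one record per index peer.

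At stake is the interpretation of the main result. Initiation is measured among those referred, so how many peers each arm referred is essential context. A difference of practical size could be reported as zero.

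**Working it through.** **1. The plan's own counts.** Ceiling: 80 × 4 = 320, or 40 × 4 = 160 per arm. The HIVST row of Table 8 agrees: "≥90% (n=144 – formal arm" is 0.90 × 160 = 144. For sample size the protocol states "If we assume that peer providers refer 75% of the targeted peer clients, this leaves us with three clients", and SAP 5.1 says "we assumed 40 clusters (index peers) per group, 3 sampling units (referred peers) per cluster". That gives 40 × 3 = 120 per arm and 240 in total, as stated.

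**2. The printed ratio.** If R clients are referred in an arm, the measure is R/R = 1 for any R above 0. The between-arm difference is 0 whatever happens.

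**3. The random effect.** With one count per index peer there is no replication within index peer. A random intercept and the residual enter each record once, as a sum. The data show the spread of that sum; splitting it rests only on the distributions assumed for the two parts.

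**4. The median on a 0–4 scale.** Assume each index peer's count is Binomial(4, p). The median is 3 when P(3 or 4) is above 0.5 and P(4) is below 0.5.

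| p | P(3) | P(4) | P(3 or 4) | Median | Mean | Total per arm |
|---|---|---|---|---|---|---|
| 0.65 | 0.3845 | 0.1785 | 0.563 | 3 | 2.6 | 104 |
| 0.80 | 0.4096 | 0.4096 | 0.819 | 3 | 3.2 | 128 |

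The median difference is 0. The mean difference is 3.2 − 2.6 = 0.6 per index peer, or 128 − 104 = 24 peers. The example is not on an edge: the median is 3 for p from about 0.62 (P(3 or 4) = 0.510) to 0.84 (P(4) = 0.498).

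**5. What a mean difference would show in the same case.** Variances are 4 × 0.65 × 0.35 = 0.91 and 4 × 0.80 × 0.20 = 0.64. SE = √((0.91 + 0.64)/40) = 0.197, so the 95% half-width is 1.96 × 0.197 = 0.39. Power ≈ Φ(0.6/0.197 − 1.96) = Φ(1.09) ≈ 86%.

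The documents give no correlation for referral, so I also multiplied the variance by 1 + 3 × ICC. At 0.05 the SE is 0.211 and power about 81%. At 0.2 the SE is 0.249 and power about 67%.

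**6. The threshold, as context.** More than 50 means at least 51, or 51/40 = 1.275 per index peer. If control referred 75%, the largest possible difference would be 160 − 120 = 40. With the intervention arm at 160, control must refer at most 160 − 51 = 109, or 109/160 = 68%.

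**The case against.** The strongest reply is that the intended measure is easy to recover. The Details column, the metric itself, the protocol's text on secondary outcomes and SAP Tables 1 and 4 all point to a count. That stands: the ratio and the binary note are drafting slips, and it would be wrong to infer that the row permits no comparison at all.

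A second reply is that the protocol's Statistical analysis section allows the provider as unit of analysis and asks for clustering adjustment only at client level. SAP 10.2 also names initiation, testing, continuation and adherence, and does not assign a model to process outcomes. This stands in part. The protocol does not require a random effect here, so the fair criticism is that no suitable estimator is named, and that the one non-binary rule on offer would be a poor choice.

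A reader might also infer that ">50 more peers" is impossible. The documents do not support that. The 75% is a sizing assumption for the initiation comparison and not a forecast of control referral. The pilot benchmark, "≥3 peers per PrEP user (n≥48", was a minimum for users who had training and kits; control providers get neither. The metric can be met once control falls to 68% or below with the other arm near its ceiling. A demanding bar is the sponsor's to set.

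**Conclusion.** The point holds and is minor. The Table 8 measure is 1 by construction, the SAP note mislabels a count, and the available median rule can report no difference when the arms differ by 24 peers.

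The median example assumes binomial counts. With stronger clustering within index peers the two medians may separate, in which case the estimate would jump to 1 against a true mean difference of 0.6. That is no better a summary. The mean-difference power of about 86% is a normal approximation, falling to 67–81% over the correlations I assumed.

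Nothing here touches the primary analysis, its power or the initiation estimate. Nor do the documents say that missing this one metric stops progression: the findings are to inform a later grant proposal, and no rule requires every row to be met.

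**What to change.** 1. In Protocol Table 8 and SAP Table 4, define the outcome as the number of clients referred per index peer (0–4), intervention minus control, and exempt it from the binary note.
2. In SAP 10.2, add one line: between-arm mean difference with 95% CI, one record per index peer, robust standard error, no random effect. The robust error allows for unequal variances when one arm sits near the ceiling, and a per-index-peer mean does not shift merely because follow-up numbers differ between arms.
3. Optionally, note beside ">50 more peers" that it equals 1.275 per index peer with 40 per arm and needs control referral of 68% or lower.

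The cost is two table cells, one footnote and one analysis line. Index peers already report the count at Month 3, so no new data are needed. Keeping the threshold moves no bar. If the sponsor prefers to restate it, the change comes after the trial began and should be dated, with a statement that arm-level data had not been seen.

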## 1. Introduction

This document (Statistical Analysis Plan, SAP) describes the planned analysis and reporting for the study titled, “Peer PrEP referral + HIV self-test delivery for PrEP initiation among young Kenyan women: randomized implementation trial,” also known as the “Peer PrEP cRCT”. This trial is a joint collaboration between the Fred Hutchinson Cancer Center (Fred Hutch) and the Jomo Kenyatta University of Agriculture and Technology (JKUAT; R00 MH121166, PI: [name]). It includes specifications for the statistical analyses and tables to be prepared for final reporting for the randomized trial.

The planned analyses described in this SAP will be included in future manuscripts. Note, however, that exploratory analyses not necessarily identified in this SAP may be performed to support the analysis. All post-hoc or unplanned analyses which have not been delineated in this SAP will be clearly documented as such in the final study reporting, manuscripts, or any other document or submission.

## 2. Study rationale

Few young women at risk of HIV infection are initiating daily, oral pre-exposure prophylaxis (PrEP) for HIV prevention in Kenya, thus we propose developing, refining, and testing a new model to increase PrEP initiation among young women at high HIV risk that has not yet been explored: peer PrEP referral + HIV self-testing (HIVST) delivery (1).

Through a pilot based on qualitative formative research and stakeholder engagement, we developed and refined an acceptable and feasible model where young (≥16 to 24 years) female PrEP users refer their peers to PrEP using materials we determine to be appropriate (e.g., pamphlets) and HIVST kits. In phase 2 of this study, we plan to conduct a 2-arm hybrid effectiveness-implementation randomized trial to test the effect of the refined peer PrEP referral + HIVST delivery model on PrEP initiation among young Kenyan women compared to informal peer PrEP referral, where young women are encouraged to refer four peers to PrEP services by word-of-mouth, as is ongoing in Kenya. We hypothesize that relative to informal, standard word-of-mouth peer PrEP referral (our control group), formalized/enhanced peer PrEP referral + HIVST delivery will increase PrEP adoption (i.e., initiation, retention, and adherence) among peers, be low cost, and have high fidelity among young Kenyan women.

## 3. Study overview and objectives

### 3.1. Study overview

**Table 1. Overview of the Peer PrEP cRCT components**

[figure not shown]
Protocol title:	Peer PrEP referral + HIV self-test delivery for PrEP initiation among young Kenyan women: randomized implementation trial
Short title:	Peer PrEP Study
Design:	This study is a hybrid effectiveness-implementation randomized trial
Population:	We will enroll two different population types in this study: 1. Index peers : (Also called PrEP users or peer providers in our formative research and pilot study). Adolescent girls and young women ≥16-24 years  old using PrEP for at least one month in the past 12 months.

	
2. Referred peers: (Also called peers or PrEP clients in our formative research and pilot study). Female peers <math>\geq 16</math>-24 years old of the index peer whom the index peer thinks has behaviors associated with HIV risk and may be interested in and benefit from daily oral PrEP.
 
16- and 17-year-olds must be emancipated minors; all participants must be able and willing to provide informed consent.

Randomization:	1:1 enhanced group: standard group
Study groups:	
Intervention: Enhanced peer referral (previously formal peer referral)
 
 
• Index peers randomized to the enhanced group will receive the package of implementation strategies below and be encouraged to refer four peers to PrEP: 
 
○ A one-day training on HIVST & PrEP and how to have conversations about and refer peers to PrEP service
 
○ PrEP informational brochures (n=4, 1 per peer)
 
○ HIVST kits (n=8, 2 per peer)
 
○ PrEP referral cards (MOH-style), with information on nearby facilities delivering free PrEP services (n=4, 1 per peer)
 
 
 
• Referred peers referred to PrEP services by index peers in this group should receive the described package of implementation strategies to support PrEP referral.
 
 
Control: Standard peer referral (previously informal peer referral):
 
 
• Index peers randomized to the standard group will be encouraged to refer four peers to PrEP services using existing informal word-of-mouth referral, common among AGYW. They will receive: 
 
○ PrEP referral cards (MOH-style), with information on nearby facilities delivering free PrEP services (n=4, 1 per peer)
 
 
 
• Referred peers referred to PrEP services by index peers in this group will be referred to PrEP services informally, as is ongoing in Kenya.
 

Sample size:	
400 enrolled index and referred peers in total*
 
 
• 80 index peers
 
• Up to 320 referred peers
 
 
*The enrollment numbers for referred peers may be lower due to challenges in getting provide their contact information at the time of peer referral. Primary outcomes among referred peers will be reported by index peers in index peer follow-up surveys.

Follow-up:	3 months from either the time of intervention delivery (index peers) or time when study staff received their contact information (referred peers)
Study sites:	Three counties in Central Kenya: Kiambu, Nairobi, and Murang'a (in the area surrounding the PHRD research clinic in Thika)
Clinical outcomes:	
 
• Primary: PrEP initiation among referred peers, as reported by index peers at 3 months
 
• Secondary: recent HIV testing (since referral) and PrEP continuation (i.e., any refilling) among referred peers, as reported by index peers at 3 months. PrEP adherence (self-reported) among referred peers, as reported by referred peers at 3 months. PrEP continuation (since referral) among index peers, as reported by index peers at 3 months.
 

Process outcomes	
 
• Number of peers referred to PrEP, reported by index peers at 3 months.
 

	
 
Linkage to care (i.e., visited a healthcare clinics), as reported by referred peers at 3 months
 
HIVST use, reported by referred peers in the enhanced group at 3 months.
 

Implementation outcomes:	
 
Acceptability, feasibility, and appropriateness measured using validated scales (reported by index peers and referred peers at 3 months). Fidelity measured by the intervention materials delivered.
 

